# Cancer Registry

All subjects participating in the study will be registered with either the for Health & Social Care Information Centre (HSCIC) for England and Wales or the Cancer Registry and Central Services Agency of Northern Ireland depending upon their place of residence. The computerised entry for each subject at the registry will be tagged to prompt notification to

the coordinating centre in the event of new cases of cancer and deaths in the study population. Women will be followed until 2024 to capture the full impact of screening on mortality due to ovarian cancer as this may not be evident in the few years immediately after screening has halted. The registry will also notify the CC of individual subjects who do not appear on the register so that further information required to trace their entry can be obtained or alternative methods of follow up employed. Individuals not identified on the register will be followed up by postal questionnaires only.

#### **Outcome's review process**

The purpose of the outcome committee's review is to verify reported or probable diagnosis of and death due to, ovarian/fallopian tube cancer.

# 1. Identification of potential ovarian/tubal cancer by coordinating centre

The Coordinating Centre (CC) is notified of new cases of ovarian/fallopian tube cancer (OC) and possible ovarian cancer by various sources.

The RC notifies the CC of all new cases of screen detected OC (and possible OC) and forwards relevant medical notes to the UKCTOCS senior research nurse or designated research associate. The RC will sometimes also notify the CC of screen negative and control arm cases where these cases are known to them. However, these volunteers do not always receive treatment at the RC hospital and will therefore not be identified through this method.

The Health &Social Care Information Centre (formerly NHS IC and prior to this, ONS) cancer registration and Death Certificates are two of the most important sources of information. Quarterly HSCIC updates are received electronically. After each\_update, a query is run to identify potential new cases of ovarian/tubal cancer. The query flags up a list of ICD-10 codes that could be related to a diagnosis of ovarian or tubal cancer (see Appendix S-III Table1)).

The cohort has also been linked to the Hospital Episode Statistics (HES) in England. HES is a comprehensive dataset of volunteers' in- and out- patient hospital admissions and corresponding disease codes from 2001-2009 and 2003-2009, respectively. HES data on the women was received by the CC in 2010. The clinical diagnosis fields of the HES dataset are searched for the ICD-10 diagnosis codes, (see Appendix S-III) and in addition, for operative procedures.

New cases can also be identified through the follow-up questionnaires, which are sent to all volunteers in both the screening and control arms. The first questionnaires were sent out at approximately 3.5 years post randomisation to the trial and the second follow-up questionnaire in 2014. A query is run, after each upload of data from returned questionnaires, to capture new cases of OC and possible OC.

The research associate may also identify cases of ovarian cancer when querying volunteers, who have been withdrawn from the trial because their ovaries have been removed. In all instances where the CC is aware that the woman has had her ovaries removed surgically, a letter and a single page questionnaire are sent to the volunteer

requesting more information about her operation when ovaries were removed. Upon receipt of volunteer's reply, the research associate contacts the volunteer's hospital consultant for further information about the operation and whether a diagnosis of cancer was made. All attempts are made to obtain histology reports of the removed ovaries.

Occasionally, the volunteer (or her relative) may inform the CC directly of her ovarian cancer diagnosis. However, usually they notify the RC.

#### 2. Review Process

Once a volunteer is "flagged up" as potentially having ovarian/fallopian tube cancer or having died due to ovarian/fallopian tube cancer, copies of all her medical notes relating to the cancer diagnosis/death are obtained from the corresponding regional centres, hospital(s) where treatment was received, GP surgeries, hospices and cancer registries.

The collected notes, arranged in chronological order and stripped of any evidence of volunteer allocation in the trial and/or screen-detection of the cancer, are presented to a member of the Outcomes Review Committee (ORC). Generally, at least three documents are required for ascertainment of an ovarian/fallopian tube cancer diagnosis or death due to ovarian/fallopian tube cancer. Where surgery has been performed, one of these documents must be a histology report. Other relevant information includes death certificates, NHS IC cancer registrations (CR), biopsy/cytology reports, diagnostic imaging results, multidisciplinary team meeting (MDT) summaries, discharge summaries, chemotherapy schedules and hospital letters. The clinical records, submitted to reviewers,

must also contain a clear letter of diagnosis by the clinical team such as an MDT review, letter to GP or hospital letter prior to chemotherapy commencement.

Upon review of the documents, the reviewer completes a trial cancer review form (CRF; see Appendix S-I)) and death review form (DRF, where applicable; see Appendix S-II)) for each volunteer. If the submitted information is deemed adequate and there is agreement between the reviewer's cancer diagnosis/cause of death assignment and either CR or death certificate (DC) registrations, the case will be considered "signed off". A signed off case will have primary cancer site, grade and stage (and cause of death, where applicable) verified. If the reviewer disagrees with either of CR/DC, the case will be forwarded to a second ORC member for an independent review. If the two ORC members are concordant in their assignments, the case will be signed off; otherwise, a third ORC member will independently review the case; and cancer diagnosis and cause of death will be signed off based on the majority reviewers' assignment. If there is disagreement between the assignments of the three ORC members, the case will be set aside for outcome committee's discussion, where two pathologists and two oncologists will review the case together and sign it off. Reviewers can also refer cases to outcome committee's discussion when they cannot independently ascertain cancer diagnosis and/or cause of death (Figure 4).

If the submitted information is insufficient for verification of cancer diagnosis/cause of death, the reviewer may request either additional information or histology slides for pathological review to determine stage/grade of diagnosed ovarian/tubal cancer. In such

cases, the UKCTOCS research associate will obtain the requested information or histology slides. Once the slides have been reviewed, the case will be re-submitted to the original reviewer with the additional histology report.

Case submitted to outcome review committee Adequate information Incomplete information for verification More information / Pathology Agreement Discrepancy with RC/DC: Independent review by 2nd with RC/DC Member Difficult case: Cannot assign -Disagreement ' Agreement Outcomes Discussion Between ORC Independent review by 3rd member members Signed off based on the majority of the Case signed off reviewers' assignment Disagreement refers to discordance with RC/DC re: C56/C57.0

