#### Primary analysis:

The primary analysis will be a direct comparison of the mortality rate of ovarian cancer:

- between the control arm and multimodal arm
- between the control arm and ultrasound arm.

Events of interest will be those deaths signed off by Outcome Review as primarily caused by ovarian cancer (ICD-10: C56) or tubal cancer (C57.0) or undesignated ovarian/tubal/peritoneal cancer. The analysis will be based on 'intention to treat', so that no allowances for non-compliance to screening will be made. Similarly for any 'contamination' that occurs. A Cox regression model will be used to model the difference in mortality rate between the control arm and each individual screen arm. Several sensitivity analyses will be performed to validate the primary outcome result.

**Secondary analyses:** This will include assessing the performance characteristics of the screening modalities, namely their sensitivity, specificity and positive predictive value, compliance with screening and complication rates resulting from trial surgery using the conventional ratios with appropriate confidence intervals.

There will be an interim analysis performed at the point where half the expected number of control group deaths due to OC (111) is reached. This will include all primary and secondary endpoints detailed above as well as intermediate endpoints for OC mortality such as stage of OC and lead time (mean duration of preclinical disease) estimated from the ratio of prevalence (at the first screen) and incidence (annual) rates of OC.

The economic analysis will be undertaken on the calculated cost-effectiveness ratios that are crucial to the trial. It will include both a within trial analysis and a modeling analysis. The within trial analysis will consider the cost-effectiveness ratios relating to protocol driven resource use. The modeling analysis will take into account standard practice which would reflect the implementation of a National Screening Programme (as this may differ

from study protocol resource utilisation), and extrapolation of trial results over a longer time frame to include lifetime benefits.

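### When the reviewer agrees with only one of cancer registration and death certificate, the two sign-off rules for the primary event give opposite instructions

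*Protocol*

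**What the plan says.** The Protocol's Outcome's review process, part 2 (Review Process), gives two rules for a case whose information is adequate.

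- **Sign-off on one review.** The condition is agreement between the reviewer's cancer diagnosis or "cause of death assignment and either CR or death certificate (DC) registrations, the case will be considered" signed off.
- **Referral.** "If the reviewer disagrees with either of CR/DC, the case will be forwarded to a second ORC member for an independent review".

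Sign-off settles the classification: "A signed off case will have primary cancer site, grade and stage (and cause of death, where applicable) verified". The Primary analysis section then takes its events from this process: "Events of interest will be those deaths signed off by Outcome Review as primarily caused by ovarian cancer", with tubal cancer and undesignated ovarian/tubal/peritoneal cancer also counted.

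The text of Figure 4 has one branch for agreement and one for discrepancy with the two sources, and a note: "Disagreement refers to discordance with RC/DC re: C56/C57.0". (The figure's RC is the registration that the body text calls CR.)

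Two safeguards precede these rules. Notes reach the reviewer "stripped of any evidence of volunteer allocation in the trial and/or screen-detection of the cancer". On evidence: "Generally, at least three documents are required for ascertainment of an ovarian/fallopian tube cancer diagnosis or death".

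**The concern.** The word for either appears in both rules with different effect. In the first, one agreement is enough to close the case. In the second, one disagreement is enough to refer it. The rules are complementary only when the reviewer agrees with both sources or with neither. With one agreement and one disagreement, the text orders both closure and referral.

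These are the cases in which a second reading is most useful, because an official source contradicts the reviewer. They also bear on the primary endpoint. A woman registered with C56, whose certificate gives a cause other than OC, may become an OC death on one opinion under the first rule and only after a second reading under the second. The reverse error is equally open: a certified OC death may be removed by one reviewer who sides with a non-ovarian registration. Two staff members following the same paragraph could handle the same case differently.

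**Working it through.** No stated sample size, power or alpha is at issue. The check sets the two rules side by side.

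**Inputs.** Both rules come from the Review Process section, the classification scale from the Figure 4 note, and the event definition from the Primary analysis section. Let a = 1 if the reviewer agrees with the CR and b = 1 if the reviewer agrees with the DC.

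- Sign off if a = 1 or b = 1.
- Refer if a = 0 or b = 0.

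**Step 1: the general condition.**

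| a (CR) | b (DC) | Sign off | Refer | Result |
|---|---|---|---|---|
| 1 | 1 | yes | no | consistent |
| 1 | 0 | yes | yes | conflict |
| 0 | 1 | yes | yes | conflict |
| 0 | 0 | no | yes | consistent |

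The rules conflict exactly when the reviewer agrees with one source only.

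**Step 2: one yes/no classification (C56/C57.0 or not), as in the Figure 4 note.** CR, DC and reviewer give 2 × 2 × 2 = 8 combinations. In the 4 where CR and DC are the same, a = b and there is no conflict. In the 4 where they differ, the reviewer must match one and contradict the other, so all 4 conflict.

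**Step 3: three classes (ovarian/tubal, peritoneal, other).** CR and DC differ in 3 × 2 = 6 ways; with 3 reviewer choices that is 18 combinations. The reviewer matches one source in 6 × 2 = 12, which conflict. In the remaining 6 the reviewer matches neither and only referral applies.

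**Step 4: item by item (site against CR, cause of death against DC).** If a woman is registered with C56 and certified as dying of something else, and the reviewer accepts both, then a = b = 1 and there is no conflict although the sources differ. If the reviewer accepts the C56 but assigns the death to OC against the certificate, then a = 1 and b = 0, and both rules apply.

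**Step 5: is there a tie-break?** None was found in the Outcome's review process section, the text of Figure 4, or the cancer and death review forms.

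**Step 6: the rule after repair.** Sign off only if a = 1 and b = 1, and otherwise refer. The conditions are then complements, and 0 of the 8 combinations in Step 2 conflict. No sample size or power figure changes.

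**Step 7: the Figure 4 note against the event definition.** The note measures disagreement on C56/C57.0. The Primary analysis also counts undesignated ovarian/tubal/peritoneal cancer. A reviewer's choice between undesignated and C80 or C48 changes event status, yet need not register as disagreement on the note's wording.

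**The case against.** The best defence is that the sentence pairs diagnosis with registration and cause of death with certificate, and that either means whichever source applies. The process covers living women, who have no certificate, and cases that arrive through hospital data or questionnaires, perhaps without a registration. This is a sensible reading and may be what was intended. It stands against any claim that the rules clash whenever CR and DC differ (Step 4). It does not settle the case where both sources exist and the reviewer accepts one and rejects the other, and the text does not state that pairing.

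A reader might also infer that one reviewer does fix OC deaths against the certificate. The text does not support that: only one of the two rules permits it, and the other sends the case on. The death review form also has a field for checking the certificate and asks for evidence of progression or of treatment complications.

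A reader might infer bias between the arms. Allocation and screen detection are removed from the notes, and generally three documents are required, so the documents give no ground for differential error. These safeguards do not, however, say which rule governs.

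A reader might try to size the effect by applying an assumed discordance rate to the planned deaths. No such rate is given, and the expected 222 control deaths per 100,000 women belong to the 7-year plan that the extended follow-up replaced.

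On Figure 4, the note is a single legend line. The table on the cancer review form appears to code undesignated cases as C56/C57/C48, so some of them may count as disagreement after all. That limb is a secondary mismatch of wording.

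**Conclusion.** The point holds in a limited form. Where the reviewer agrees with one of CR and DC and disagrees with the other, the Protocol prescribes both single-review sign-off and referral, without precedence. The sign-off defines the primary event, so the number of opinions behind some events is undetermined.

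The logical extent is exact: every case with one agreement and one disagreement, which is 4 of 8 combinations if diagnosis and cause are collapsed to one yes/no classification. These counts describe the rules and say nothing of how many women are affected. That frequency is not given, so no change in event counts, hazard ratio or power can be stated. The consequence is inconsistent adjudication and possible misclassification of the primary event in either direction. The conclusion assumes that no separate committee procedure, not shown here, already supplies the tie-break.

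**What to change.** Replace the two sentences with one rule: a single review suffices only if the assigned primary site agrees with the CR and the assigned cause of death agrees with the DC, each where that source exists; any case with a disagreement goes to the second committee member. The qualification on existing sources is needed, since otherwise every living or unregistered woman would be sent to second review.

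Reword the Figure 4 note so that disagreement means any difference that changes primary-event status: C56, C57.0 or undesignated ovarian/tubal/peritoneal cancer against all other codes.

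Before the primary analysis, query the signed-off cases for those in which the reviewer disagreed with one source and only one review was done, and send those to second review.

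The cost is a protocol wording change, one database query and a limited number of extra reads by the existing committee, using a referral step already in the plan.

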**Figure 4: Outcome Review Process** 

# Morbidity and serious adverse reactions

RC: HSCIC Registration

A copy of the operative and other relevant pages of the hospital notes of women who undergo trial surgery will be obtained. A senior trial gynaecological oncologist blinded to

the randomisation group will confirm all surgical complications. Suspected unexpected serious adverse reactions will be reported within 7 days using a defined protocol and specific form (Appendix U). Complications related to screening and resulting from trial surgery will be presented regularly to the Data Monitoring and Ethics Committee.

# Psychosocial study:

All consenting women will complete psychosocial baseline questionnaires at randomisation (Appendices E-J) These include an examination of their knowledge, beliefs and attitudes to ovarian cancer screening and standardised questionnaires including the General Health Questionnaire 12 (GHQ12), Speilberger Trait Anxiety Inventory (STAI) and Fallowfield's Sexual Activity Questionnaire (SAQ). This information is entered into the study database if the women are subsequently randomly chosen for longitudinal follow-up (250 women in each screening arm and 500 in the control arm) or if any woman's screening results are not straightforward. Volunteers will complete a set of postal questionnaires annually for 6 years to assess their emotional well-being, psychological functioning, sexual activity, and the acceptability of the screening process after each screen. Women will also complete questionnaires if they undergo surgery and again if the surgery reveals that they have ovarian cancer. These women will then be followed longitudinally at 6 months post-surgery.

#### Serum bank:

Excess serum will be stored for future use in ethically approved studies for early detection and treatment of disease. A semi-automated system will aliquot this serum into 500 microlitre straws which will then be heat sealed, barcoded and stored in special containers

in liquid nitrogen tanks. Once filled, the tanks will be transported to an offsite cryonic biorepository.

# Statistical analysis plan

The primary outcome measure in UKCTOCS is ovarian cancer (OC) mortality and the primary comparison is based on an 'intention to treat' analysis between control (C) group and each of the screened groups (M and U). In the UK, there are approximately 37 deaths from ovarian cancer per 100,000 women aged 50-74 per year. Assuming an attrition rate of 4% per year (75% of patients followed up for the full 7 year period) gives a mean of 6 person years of observation for each patient randomised, and thus an expected number of deaths from ovarian cancer in the control group of 222 per 100,000 women randomised. The event of interest, death from ovarian cancer, is rare and so it is assumed that the observed number of deaths in each group follows a Poisson distribution. Under these assumptions, a total sample size of 200,000 (100,000 controls, 50,000 in each screening group) followed for 7 years from randomisation would give > 80% power at the (two-sided) 5% significance level to detect a reduction of 30% in each of the screened groups (C vs M or U).

The operating characteristics of the two screening arms are different. It is important to note that if one comparison is significant and the other is not, this result does not necessarily imply that one method is significantly better than the other. Only the direct comparison between the two methods will address this issue. The trial has at least 70% power to detect a difference in OC mortality between the two screening groups of 30% or more. However, if as anticipated the difference in OC mortality between the two screened groups

is modest then this study will have limited power to detect such differences e.g. 35% power to detect a difference of the order of 20%. The choice of screening strategy will then be based on other outcome measures such as sensitivity, positive predictive value, morbidity, quality of life and health economics.

Randomisation to UKCTOCS was completed in October 2005 and in 2007, with women having completed a median of approximately 3.5 years in the study, it was possible to review mortality in the control arm. The expected number of control group deaths (ED) based on mortality statistics from ONS 2004 was recalculated with more precision taking into consideration several factors.

- (1) Age-group specific mortality rates based on the age at randomisation of the 202,638 women and the increasing age of the women as the trial progresses
- (2) Reduction in OC deaths due to the eligibility criteria in the early years of the trial. Deaths in any particular year from ovarian cancer occur largely in women diagnosed with the disease in the preceding 2-3 years. Based on eligibility criteria women with ovarian cancer were not able to join the trial.
- (3) True attrition rate to follow up Follow up was via ONS flagging and few women withdrew from flagging even if they withdrew from screening. As a result, the original 4% annual attrition rate was found to be conservative. So in place of an attrition factor, an adjustment was made for a mortality factor of deaths from other causes that reduces the effective population at risk from ovarian cancer.

This analysis identified a shortfall in number of observed deaths (OD) in UKCTOCS participants compared to age adjusted expected deaths (ED). The overall Standardised

Mortality Ratio (SMR - ratio of observed versus expected deaths expressed as a percentage) was 31.6 (95% CI 30.1, 32.7) suggesting that there was a 'healthy volunteer effect (HVE). The SMR for OC mortality was 58.31(95% CI 40.4, 81.5). When the SMR was calculated for each year from randomisation, it gradually increased suggesting that the HVE became less of a factor as time from randomisation increased. On this basis, a reasonable estimate of the SMR for OC mortality for the trial was taken as 65. An OC SMR of 65 would have a significant impact on power calculations. It would have reduced the power to detect a 30% reduction in mortality between control and one of the screen arm (C vs M or U) to 53.7% versus the original estimate of 80%.

After exploring various options to increase sample size, it was finally decided to alter the trial design to extend follow up on all women to 31st December 2014. Based on randomisation date, this would result in individual women being in the trial for 9 to 13 years. In the study groups (M and U groups) the number of annual screens was extended till 31st December 2011 such that women underwent 7 to 11 screens (compared to the original 6 screens) depending on date of randomisation. Women in the study groups would be followed up for at least 3 years from their last annual screen. The design provides the power to detect a 30% reduction in mortality between control and one of the screen arm (C vs M or U) of >80% as originally envisaged.

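### The 70% and 35% power figures for multimodal versus ultrasound assume, without saying so, that one strategy has no effect; even then a 30% difference gives about 68%, not at least 70%

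*Protocol*

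**What the plan says.** All the relevant text is in the protocol's Statistical analysis plan section. The death count is built from "approximately 37 deaths from ovarian cancer per 100,000 women aged 50-74 per year", and an attrition allowance that "gives a mean of 6 person years of observation for each patient randomised", leading to "an expected number of deaths from ovarian cancer in the control group of 222 per 100,000 women randomised". Deaths are taken as Poisson, with "a total sample size of 200,000 (100,000 controls, 50,000 in each screening group"). For each screened arm against control the section claims more than "80% power at the (two-sided) 5% significance level to detect a reduction of 30% in each of the screened groups (C vs M or U").

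For M against U it then states: "The trial has at least 70% power to detect a difference in OC mortality between the two screening groups of 30% or more". It adds that a modest difference is anticipated, that power for such a difference is limited, and illustrates this with "35% power to detect a difference of the order of 20" per cent. In that situation, "The choice of screening strategy will then be based on other outcome measures such as sensitivity" and several others it lists.

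Later in the same section the original attrition rate is called conservative, ovarian cancer mortality is found to be below expectation, and follow-up is extended to 31 December 2014. Power above 80% is restated for control versus M or U. Power for M versus U is not restated, and no expected number of deaths is given for the extended design.

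**The concern.** A power figure for two active arms needs a death rate for the less effective arm and a scale for the difference. The section gives neither. The quoted figures fit only a less effective arm at the unscreened rate, whereas the trial is designed around a 30% reduction in each screened arm. With fewer deaths in both arms, a given relative difference is harder to detect. For a relative difference, the quoted case is therefore the most favourable, although the text presents it as a minimum.

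The section itself says that only the direct comparison can show whether one strategy is better than the other. A reader weighing an M versus U result will use these figures to judge how informative it is, so they should be reproducible and their assumptions visible.

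**Working it through.** **Inputs** (all from the Statistical analysis plan section): 37 deaths per 100,000 per year; mean 6 person-years; 50,000 women in each of M and U; Poisson deaths. The two-sided 5% level is stated for the control comparisons and is assumed here for M versus U, for which none is given.

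**Expected deaths at the unscreened rate:** 37 × 6 = 222 per 100,000, so 111 per 50,000.

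**Formula.** With expected deaths A in the less effective arm and B in the other, equal arm sizes:

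power = Φ[(A − B)/√(A + B) − 1.96]

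**Step 1: the protocol's 35%.** Less effective arm at the unscreened rate, 20% difference: A = 111, B = 88.8. (22.2)/√199.8 = 1.571, and Φ(1.571 − 1.96) = 34.8%. Other normal approximations give 34.7 to 35.1%. The stated 35% is reproduced, which identifies the reference rate: one screened arm has no benefit.

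**Step 2: the protocol's 70%, same basis.** A = 111, B = 77.7 (188.7 deaths in all).

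- Difference of counts: 33.3/√188.7 = 2.424; Φ(0.464) = 67.9%
- Square root: √2 × (√111 − √77.7) = 2.434; 68.2%
- Log rate ratio: 0.3567/√(1/111 + 1/77.7) = 2.411; 67.4%
- Schoenfeld: 0.3567 × √(188.7/4) = 2.450; 68.8%
- Conditional exact test: 65.5%

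None reaches 70%. The difference formula needs about 117 deaths in the less effective arm; Schoenfeld needs 195 deaths over the two arms.

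**Step 3: both strategies effective, 7-year count.** Difference formula, with the Schoenfeld value in brackets for the percentage-point column:

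| Reduction in less effective arm | 30% relative to that arm: deaths, power | 20% relative: power | 30 points of control mortality: deaths, power |
|---|---|---|---|
| 0% | 111 v 77.7, 68% | 35% | 111 v 77.7, 68% (69%) |
| 10% | 99.9 v 69.9, 63% | 32% | 99.9 v 66.6, 73% (74%) |
| 20% | 88.8 v 62.2, 58% | 29% | 88.8 v 55.5, 79% (81%) |
| 30% | 77.7 v 54.4, 53% | 26% | 77.7 v 44.4, 85% (87%) |

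The two scales coincide when the less effective arm is at the unscreened rate, so the match at 35% does not show which scale was meant.

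**Step 4: extended follow-up.** The protocol gives no death count, so this is conditional on an assumption: control deaths just sufficient for 80% power, control versus one screened arm, at a 30% reduction. With Schoenfeld and 2:1 allocation, total deaths needed = (1.96 + 0.8416)²/[(2/9) × 0.3567²] ≈ 278, of which 278/1.35 ≈ 206 are in control, or 103 per 50,000.

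- One strategy ineffective: 103 × 1.7 ≈ 175 deaths; 0.3567 × √(175/4) = 2.36; power about 65%
- Less effective arm at a 30% reduction, relative difference: 175 × 0.7 ≈ 122 deaths; 0.3567 × √(122/4) = 1.97; power about 50%

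Other approximations need up to 238 control deaths and give up to about 70% and 55%. Power for the control comparison above 80% would raise both.

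**The case against.** The best defence is that 70% is a rounded figure built on rounded inputs. That largely stands for its size. Schoenfeld gives 68.8%. With continuous 4% attrition (6.09 person-years) and the 202,638 women actually randomised, there are 6.09/6 × 202,638/4 × 0.00222 ≈ 114 deaths per arm at the unscreened rate, and the normal approximations give about 69 to 70%. The text also says 30% or more, so the shortfall is at exactly 30%. What does not stand is the claim of a minimum, which no method reaches on the section's own inputs.

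Second, M versus U is not a primary comparison, did not set the sample size, and the section openly says power is limited for modest differences. This stands and limits the importance. The 35% used to illustrate that limit, however, carries the same unstated assumption.

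Third, the 111 deaths belong to the superseded 7-year plan. With no attrition at all (an assumption: 37 × 7 = 259 per 100,000, or 129.5 per arm), power would be about 74 to 75%. Against that, the section also replaces attrition with a factor for deaths from other causes and adopts a standardised mortality ratio of 65 for ovarian cancer. Neither direction can be settled without an expected count for the extended design.

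Two stronger readings are tempting and are not supported. One is that power is 53 to 58% whenever both strategies work. This needs a relative difference and a 20 to 30% reduction in the less effective arm; a 10% reduction gives 63%, and the percentage-point scale gives 73 to 87%. The other is that the protocol would treat a non-significant M versus U test as showing no mortality difference. It does not say so: it turns to other outcomes because it acknowledges that mortality may not discriminate.

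**Conclusion.** The point holds in a limited form. Both M versus U figures rest on an unstated assumption that one strategy leaves mortality unchanged. Under it the 35% is right, and the 70% should be about 68%, an excess of 1 to 3 points by normal approximations and 4.5 by the exact test. The larger issue is the missing definition: depending on the scale, a 30% difference with both strategies effective has power anywhere from about 53% to about 87% when the less effective arm lowers mortality by 10 to 30%. These figures assume two-sided 5% and the original 7-year count. The power of the current design for this comparison cannot be derived from the protocol. The primary comparisons are not affected.

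**What to change.** In the Statistical analysis plan section:

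1. Replace the 70% claim with: about 68% power for a 30% difference if one strategy has no effect on mortality. Attach the same condition to the 35%.
2. State whether the difference is relative to the other screened arm or in percentage points of control mortality.
3. Add the power when both strategies work. If the difference is relative and the less effective arm achieves the 30% design reduction, this is about 53% for a 30% difference and 26% for a 20% difference.
4. Label these as figures for the original 7-year design.
5. Recompute M versus U power from the deaths expected under follow-up to the end of 2014, and give that count. If it only just yields 80% for control versus M or U, expect about 65% with one strategy ineffective and about 50% with the less effective arm at a 30% reduction (up to about 70% and 55% by other approximations).

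The cost is a few sentences and one calculation, with no change to design or analysis. The downside is that a stated figure becomes less favourable.
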